The traditional Life Review Therapy¹⁷ uses an 8-week, structured approach, with each session focused on a period of the life span, such as, childhood, adolescence, and so on. The intervention is often applied chronologically, but with flexibility for clinical judgements to explore other time periods that may arise for patients. For this proposal, Life Review Therapy will be adapted to be delivered dyadically, by the PI, a licensed mental health counselor and other trained clinicians with expertise in care of older adults, specifically for the older patient with advanced cancer and cognitive impairment and caregivers at risk or experiencing loneliness. The Dyadic Life Review (DLR) intervention will be delivered by one of three licensed mental health clinicians via videoconferencing over eight sessions. The goal of DLR is to enhance the dyad's communal coping and thereby reduce the loneliness and relationship distress experienced by both the older patient and caregiver. Communal coping is a process that enhances the dyad's joint resilience in supporting and managing the illness.⁶ Life review therapy has been found to reduce depression in older adults¹⁴ and promote emotional health and quality of life in patients with cancer in palliative care.¹⁸ Life review therapy combined with memory training has shown improved emotional health and cognitive functioning in older patients with cancer.¹⁶ Reminiscence therapies, which have similar processes and mechanisms to life review therapy improves cognitive functioning, anxiety, and depression in older adults with cognitive impairments.¹⁹ The vulnerable population of older patients with cancer and cognitive impairment may benefit from a DLR intervention as the intervention supports the patient/caregiver dyad in promoting communal coping, reducing loneliness and distress in both patients and caregivers, and supporting cognitive functioning in patients.

2.4 *Heart Rate Variability and Psychosocial Assessments:*

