4.2 STUDY INTERVENTIONS

DLR will consist of 8 sessions delivered by a trained licensed clinician (i.e, the PI or other trained clinician) via video-conferencing in weekly sessions of 60 minutes. Each session will facilitate a recall of each phase of life (Table 1). The patient and caregiver will each be asked structured questions to prompt reminiscence of memories from that phase of life. The DLR intervention guide attached to this protocol provides a framework of questions for each session, which follow the current standardized Life Review Handbook.²⁰ The guide acts as a framework, interventionist are able to use clinical judgment to prompt further or ask follow the patient and caregiver if pertinent events are being recalled outside of that time period. This will provide data to examine the feasibility of the DLR intervention and adapt and refine the intervention to the study's target population. Additionally, the patient and caregiver will be asked to recall if either the patient's or caregiver's recalled memory parallels the other's experiences (e.g. To Caregiver: "Does any aspects of [patient's] experience make you think of your own experiences around that time period?"). The fourth session will review recalled memories and focus on promoting communal coping in the present by drawing parallels of strength and resilience to managing MCI and cancer. The final session will review shared memories, from time periods the dyad was together, to enhance communal coping through connecting

shared memories. Each session will have flexibility for clinical judgement.

Table 1: Intervention Overview

Week	Session Life Period
1	Childhood
2	Adolescence
3	Young Adulthood (20-35 years)
4	Mid-Intervention review and dyadic processing
5	Mid-life (35-50 years)
6	Earlier later life (50-65 years)
7	Later life (65 years +)
8	Final review of shared memories and dyadic processing

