Experience (PEACE)		coping with an illness
Control Preference Scale	Exploratory Aim 1.5.2: communal coping domain	Measurement of perceived control in how people make treatment decisions with life-threatening disease
Inclusion of Other in Self	Exploratory Aim 1.5.2: communal coping domain	Perceived closeness the respondent feels with another person
Interpersonal Needs Questionnaire	Exploratory Aim 1.5.2: communal coping domain	Relationship belonging and perceived burden

Heart Rate Variability (HRV) will be calculated with the ambulatory monitoring heart-rate device Firstbeat Bodyguard 2® that measures RR intervals with a rating sample of 1 ms. The device utilizes a valid and reliable method for sampling RR intervals and provides software to analyze the raw data. We will calculate two time and frequency domain measures of HRV: SDNN (the standard deviation of all normal RR intervals measured between consecutive sinus beats), and RMSSD (the root mean square of successive differences between adjacent normal R-R intervals). In addition, we will measure frequency domain measures, natural log of high frequency (HF, total spectrum power of all NN intervals between 0.15 to 0.4 Hz) for vagal tone/RSA, natural log of low frequency (LF, total spectrum power of all NN intervals between 0.04 to 0.15 Hz), and LF/HF ratio. The use of HRV in this study will be to explore the feasibility of collecting HRV data via telehealth in this method and with this included dyad population. Additionally, there are links between HRV and stress management and emotional regulation.²⁰ This exploratory measure will provide information about HRV, stress management, and emotions in older patients with cancer and their caregivers to improve the intervention and power future studies.

Time Point 1 Measures: Patients and Caregivers will complete the baselines, time point 1 measures within two weeks of beginning their DLR intervention.

Time Point 2 Measures: The same measures provided at baseline, will be repeated within two weeks after the conclusion of the DLR intervention.

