Semi-Structured Interviews: The in-depth interviews with the patients and caregivers (interviewed separately) will focus on patient and caregiver experiences before, during, and after the telehealth DLR intervention. Patients and caregivers will be interviewed separately to ensure that each partner has a chance to disclose feelings and experiences without being censored by the other partner. Interview transcripts for a dyad will be compared later to establish common themes.

8.2 Study Procedures:

- **After Informed Consent:** Immediately after informed consent, the UBACC will be administered to determine capacity to consent. the study coordinator or PI will provide patients and caregivers with a HRV device to bring home. If patients are unable to bring the HRV device home, study staff will mail HRV device to patient/caregiver with return address envelope. This is an exploratory aim to explore the feasibility of collecting HRV with older patients and caregivers in this way. Patients and caregivers will then return the

HRV device at their next clinic visit or mail back in provided return address mailer.

- Heart Rate Variability Collection (HRV): Study staff will coordinate a zoom call with the patient and caregiver to demonstrate how to use the HRV device. Patient and caregivers will each take turns using the HRV device. Patients and caregivers will separately follow the following procedures when wearing the HRV device:
 - set timer for 20 minutes
 - sit in comfortable position
 - quiet space with no distractions
 - dimly lit room
 - no use of phone or any devices
 - maintain normal breathing

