- Baseline: Following informed consent, patients and caregivers will undergo Time Point (TP) 1 measures. Patients will be provided a data-enabled tablet with HIPAA-compliant video-conferencing application and instructed on its use, along with tablet instructions. The study coordinator will assign each dyad a unique meeting ID number within the table instruction manual. This ID number will allow the dyad to log in to the video-conferencing application for each session. The study coordinator will train and support participating dyads on how to use the tablet and video-conferencing application. If patients and caregivers consent to have sessions and interviews recorded, this will be done through a HIPAA-compliant zoom software. If participating dyads do not have access to internet, a data plan will be provided for purpose of the study. No data will be stored on the tablet. At completion of the study, participants will return the tablets to the study coordinator. If tablets are lost or stolen, no PHI will be stored on the tablet, so this will not be accessible. The participants will contact the study coordinator with any concerns about the tablets. If a tablet is broken during the course of the study, another tablet will be provided.
- Intervention Period: The intervention period is 8 weeks; eight weekly 60 minute sessions will be delivered through video-conferencing. The sessions will be audio-recorded to ensure fidelity. Interventionist may use their clinical judgement to modify session lengths or shift session topics based on patient and caregiver expressed needs during sessions.
- Follow-up: Within 2 weeks of intervention completion (weeks 9-10), patients will be administered the UBACC to determine the patients maintained capacity to consent through the duration of the study; patients and caregivers will undergo TP 2.
- Patient and Caregiver measures will be performed by the PI or a trained study coordinator. TP1 and TP2 measures can be completed either in person or through videoconferencing. Study staff will score assessments and enter into a REDCap database.
- Semi-structured interviews: 80 separate patient and caregiver interviews (from 40 dyads) will be conducted by the PI or a trained study coordinator within 2 weeks after completion of the intervention. Interviews will be audio-recorded, in a private space, by telephone with the patient and caregiver separately.

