16. DATA ANALYSIS PLAN

16.1 Sample Size Considerations: In order to assess feasibility, using a reference of 0.5 for consent and adherence rate, 40 dyads would achieve 83% power using a one-tailed test at significance of 0.05. The quantitative data will be used to guide sample size calculations for a future randomized pilot. Therefore, a sample of 40 patient/caregiver dyads will support the assessment of feasibility of the telehealth DLR with older patients and caregivers and allow for thematic saturation through qualitative semi-structured interviews.

16.2. Analysis of Aims:

16.2.1 Primary aim: To evaluate the feasibility of enrolling and delivering the telehealth DLR intervention, we will calculate proportion of: 1) approached patient/caregiver dyads who enrolled (70%); 2) enrolled dyads who completed all 8 DLR sessions (70%); and 3) general acceptability of the DLR intervention by patients and caregivers. General acceptability will be examined through coding of transcribed semi-structured interviews from the 40 dyads (separate interviews for patients and caregivers; 40 patient interviews and 40 caregiver interviews). A sub-group analysis will examine any differences between older patients with only advanced cancer and their caregivers and older patients with both advanced cancer and MCI and their caregivers in enrollment, adherence, and acceptability.

16.2.2 Secondary and Exploratory Aims: To examine the pre-post change in caregiver psychological distress, we will utilize a regression analysis that will include the pre-measurement of caregiver distress as a covariate. We will also include gender and income as covariates in this model. A regression analysis will also be used to examine changes in the exploratory measures using the same covariates. A sub-group analysis will compare the difference in changes from pre to post intervention between dyads that include older patients with only advanced cancer and dyads with older patients with both advanced cancer and MCI.

16.2.3 Mixed Methods Aim:

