Qualitative Data Analysis: Semi-structured interviews will be audio-recorded and transcribed into MAXQDA software for coding and analysis. Abductive analysis will be used to code transcribed interviews and extract themes. Two independent coders will code the data until thematic saturation is achieved. Coding will be compared and discrepancies resolved through an iterative process and achieving consensus. Semi-structured interviews will gather information about the acceptability of the intervention, perceptions of the dyadic approach to the interventions, and evaluate patient and caregiver perceptions of communal coping. A sub-group coding analysis will be performed to examine any differences in responses between older patients with only advanced cancer and their caregivers and older patients with both advanced cancer and MCI and their caregivers.

Integration: Qualitative and quantitative data, including baseline and follow up measures and

transcribed semi-structured interviews, will be integrated to develop a more complete understanding of the feasibility of a telehealth DLR intervention in this unique population and to gain understanding of the patient and caregiver experiences and gather thick descriptions about barriers and facilitators for the intervention. The qualitative data can provide explanatory data for any changes in the quantitative measures from pre to post intervention for both patients and caregivers.

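### Section 8.2 lets the PI, who also delivers DLR, conduct the acceptability interviews of dyads the PI has treated

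*Combined protocol and SAP*

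**What the plan says.** **Who delivers the intervention.** Section 2.3 names the PI and other trained clinicians, and says DLR is "delivered by one of three licensed mental health clinicians via videoconferencing over eight sessions". Section 4.2 repeats the PI's role: "DLR will consist of 8 sessions delivered by a trained licensed clinician (i.e, the PI or other trained clinician".

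**Who interviews.** Section 8.2 has the interviews "conducted by the PI or a trained study coordinator within 2 weeks after completion of the intervention". The other DLR clinicians are not named as interviewers. The same section lets the PI or the coordinator perform the patient and caregiver measures, although Section 8.1 describes the questionnaires as mainly completed by participants themselves in REDCap.

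**What rests on the interviews.** Section 16.2.1 lists acceptability with the enrolment and adherence rates under the primary aim, and examines it through "coding of transcribed semi-structured interviews from the 40 dyads". Section 1.2.1 likewise takes acceptability from the interviews. No other acceptability measure is planned.

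**Safeguards given.** Section 8.1 interviews patient and caregiver apart "to ensure that each partner has a chance to disclose feelings and experiences without being censored by the other partner". Section 16.2.3 adds: "Two independent coders will code the data until thematic saturation is achieved".

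**Timing of follow-up.** Section 8.1 says of Time Point 2 (TP2): "The same measures provided at baseline, will be repeated within two weeks after the conclusion of the DLR intervention". Section 8.2 times TP2, the interview and the follow-up heart rate variability (HRV) recording from completion of the intervention, and places TP2 at weeks 9-10.

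**The concern.** The script asks participants what they disliked, what limits they saw and what they would change. Someone who has spent up to eight one-hour sessions with a therapist may find it harder to answer such questions frankly when that therapist is asking. The plan accepts that the listener can affect disclosure, because it separates the partners for that reason. It takes no matching step for the treating clinician.

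One of the three primary feasibility measures is at stake. Coding cannot recover what a participant did not say, so the gap cannot be repaired at analysis. The mixed methods aim also uses these interviews to explain changes, or lack of change, in the quantitative measures, so any reticence would carry over there. TP2 is less exposed because most of it is self-completed.

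**Working it through.** **1. The plan's own count.** Forty dyads are enrolled (Section 4), with one patient and one caregiver interview each: 40 × 2 = 80. This agrees with Section 8.2 (80 interviews from 40 dyads) and Section 16.2.1 (40 patient and 40 caregiver interviews).

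**2. Roles side by side.**

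| Task | PI | Coordinator | Other DLR clinicians |
|---|---|---|---|
| Deliver DLR (2.3, 4.2) | yes | not named | yes |
| Conduct interviews (8.2) | yes | yes | not named |

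The overlap is therefore confined to the PI. No passage limits it to dyads treated by someone else.

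**3. What each safeguard covers.** Separate interviews remove the other partner from the conversation. Two coders protect the reading of the transcript. Neither separates therapist from interviewer.

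**4. How many interviews could be affected.** Let d be the number of dyads the PI treats and f the fraction of their interviews the PI conducts. The share of all interviews done by the treating clinician is 2df / 80 = df / 40. The documents give neither d nor f. Assume an even split among three clinicians, with the PI as one of them:

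- d = 40 / 3 = 13.3 dyads, which is 2 × 13.3 = 26.7 interviews.
- f = 1 (PI does all interviews): 26.7 / 80 = 33%.
- f = 0.5 (PI does half, at random): 13.3 / 80 = 17%.
- f = 0 (coordinator does all): 0%.

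A larger or smaller PI caseload changes these shares in proportion. They count exposed interviews and do not measure bias.

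**5. Early stoppers.** At the 70% adherence target, 0.70 × 40 = 28 dyads complete all 8 sessions and give 28 × 2 = 56 interviews. The other 80 − 56 = 24 planned interviews must come from dyads that missed at least one session. The planned count therefore already takes in non-completers. A dyad that misses one session but attends the last still fits the follow-up window. Only a dyad that stops early and stays in the study has no time point stated for it. Section 13 deals with leaving the study, not with stopping sessions. Script item 9 assumes that the second half was attended, and no item asks why sessions stopped.

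**The case against.** The best case for the plan is that this is a design preference. Section 8.2 permits a coordinator to do every interview, the other DLR clinicians are not named as interviewers, and the script openly asks for criticism. The affected share runs from none to about a third under an assumed split. The proposed substitute is not a stranger either: the coordinator is in phone contact throughout (Section 3.3) and trains dyads on the tablet (Section 8.2).

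Much of this stands. The text says the PI may interview, not that the PI will, and the coordinator is only a more distant listener. But a permission without limits is no safeguard, and a script that invites criticism does not change who is asking. The plan's own reason for separating partners applies here too.

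A reader might go further in two ways, and the documents support neither:

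- **That acceptability will be overstated.** Nothing in the documents gives the size or direction of an interviewer effect.
- **That early stoppers are left out of follow-up, so that results describe finishers only.** The plan counts 80 interviews from all 40 enrolled dyads. Section 7.7 keeps consenting patients in the study for 14 weeks without a condition on sessions attended. Section 8.2 sets an 8-week intervention period with follow-up at weeks 9-10, so completion can be read as the end of that period. Section 16.2 defines no completer-only analysis set. The script's open questions on dislikes, length and suitability, with probing, could also bring out reasons for stopping. What is missing is a sentence on timing and a direct question.

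**Conclusion.** The point holds for the interviewer. The plan permits the PI to interview dyads the PI treated, on a primary measure with no other source, and its safeguards do not reach that situation. Under an even split among three clinicians, about 27 of 80 interviews are open to it. The actual number depends on caseload and interviewer allocation, which the documents do not give. The effect on answers cannot be quantified. This does not invalidate the trial: it is an inexpensive improvement worth making before interviews begin.

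The follow-up wording for dyads that stop sessions early is a minor clarification and carries no weight in this conclusion.

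**What to change.** **Main change, Section 8.2.** State that for dyads treated by the PI, the trained study coordinator already named there conducts the semi-structured interviews and any TP2 measures that are not self-completed.

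**Minor clarification, Sections 8.1 and 8.2 and the script.** Add one sentence saying that dyads that stop sessions early but remain in the study are also followed at weeks 9-10 (TP2, interview and HRV), subject to the existing capacity rule in Sections 5.5 and 8.2. Add one script question on why they stopped. The adherence definition and the withdrawal rules stay as they are.

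**Cost.** The change needs protocol wording, one script question and more coordinator time: about 27 interviews under the even split, fewer in net terms if the coordinator would have done some of them anyway. The interviews are already planned, and Section 12 already ties a $40 payment to the post-intervention measures and interview. Because the coordinator is also known to participants, the problem is reduced, not removed.

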9. RISKS TO SUBJECTS

The potential risks to study participants are minimal for all procedures. For research assessments (self-report questionnaires and semi-structured interviews), the primary risks are invasion of privacy, breach of confidentiality (if safety issues are detected), or mild reactions of distress or fatigue. All assessment measures and procedures have been safely used previous research with older adults; no sustained negative effects from assessments are expected, but negative outcomes cannot be ruled out. For the DLR intervention, the primary risks are emotional distress or fatigue and potential loss of privacy. Regarding distress and fatigue, subjects may think about stressors, negative life events, and caregiving burden/distress; they will receive support from the interventionist for such experiences. No sustained negative effects are expected, but negative outcomes from behavioral interventions cannot be ruled out. Regarding privacy, given the videoconferencing modality, participants will be given information upfront about risks to privacy and instructed on actions they can take to protect their privacy.

10. POTENTIAL BENEFITS TO SUBJECTS

Subjects may benefit from participating in research interviews and completing the questionnaire measures, as these assessments provide them with the opportunity to be carefully listened to and comprehensively evaluated. They may further benefit from feelings of altruism connected with participation in research designed to better understand the mental health needs and experiences of community-residing older adults. Study subjects who receive DLR may benefit as this intervention targets loneliness, which is a significant risk factor for reduced well-being, morbidity and mortality.

11. COSTS FOR PARTICIPATION

There are no costs to the participants for participating in this study.

12. PAYMENT FOR PARTICIPATION

The patient and caregiver will each receive \$80 (\$80 for patients and \$80 for caregivers; \$160 total for dyad/pair) total for their participation in the study. Patients and caregivers will each receive \$40 for their time during informed consent and baseline measures. Patients and caregivers will then each receive \$40 for completion of the post-intervention measures and interview. Patients and caregivers will be paid using the Advarra/OnCore Clinical Trial Management System (CTMS). If patients and caregiver choose to enroll, they will be provided instructions during informed consent to enroll in the Advarra/OnCore CTMS.

